7.10 Duration of Follow Up

Subjects will be followed for 3-months after receiving treatment or until death, whichever occurs first. Subjects removed from study for unacceptable adverse events will be followed until resolution or stabilization of the adverse event.

7.11 Measures to Minimize Bias: Randomization and Blinding

The investigator and co-investigators are blinded to the randomization schema and treatment. The randomization schema was developed by [name] and [name] in the Division of Biostatistics and Epidemiology, Department of Healthcare Policy and Research. They have shared the schema with the Investigational Pharmacy who draws up the appropriate study drug for the subject and is picked up by the blinded study team. After all subjects are enrolled and have completed follow-up, the study team will be unblinded.

Once the study has been fully closed to enrollment and all data collection has been completed, all participants who received study treatment will be unblinded. The rationale for this is to provide participants with the appropriate information about their treatment while on study so they can make decisions about future treatment and management of their TMJ. Unblinding will occur via email or mail (if email address is not available to the study team). The unblinding text will be submitted to the IRB for review and approval before use.

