To assess the difference in proportion of adverse events between the botulinum toxin A and placebo groups, either the chi-square or Fisher's exact test will be used, as appropriate. All p-values will be two-sided with statistical significance evaluated at the 0.05 alpha level. Ninety-five percent confidence intervals (95% CI) will be calculated to assess the precision of the obtained estimates.

All analyses will be performed in SAS Version 9.4 (SAS Institute Inc., Cary, NC). Note: This section was drafted in conjunction with [name] and [name] in the Division of Biostatistics and Epidemiology, Department of Healthcare Policy and Research. They will be aiding in protocol design and development, data management, study implementation, study monitoring, and data analysis and reporting.

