12.4 Analysis of Endpoints

12.4.1 Analysis of Primary Endpoints

To assess the primary endpoint of improvement of pain on a visual analog scale (VAS) between pre-op, 1, 2, and 3 months post-op, a repeated measure of analysis of variance will be performed with one between subject factor (botulinum toxin A versus placebo) and one within subject factor (time). In the event of significant loss to follow-up, we will explore the use of a linear mixed model to assess the independent effect of the study group on VAS over the study visits.

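### Section 7.11 allows the study team to be unblinded when follow-up ends, without first requiring that adverse-event windows and queries are closed, the database is locked and the analysis is fixed

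*Combined protocol and SAP*

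**What the plan says.** Section 7.11 gives two points for end-of-study unblinding. For the team: "After all subjects are enrolled and have completed follow-up, the study team will be unblinded". For participants: "Once the study has been fully closed to enrollment and all data collection has been completed, all participants who received study treatment will be unblinded". Neither is tied to query closure, a lock or a finalised analysis, and the available text mentions no database lock anywhere.

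On who is kept blind, 7.11 says: "The investigator and co-investigators are blinded to the randomization schema and treatment". Statisticians are not listed. The schema was developed by two people "in the Division of Biostatistics and Epidemiology, Department of Healthcare Policy and Research", and "They have shared the schema with the Investigational Pharmacy who draws up the appropriate study drug for the subject". Section 12.1 says that two people in the same division will assist with "protocol design and development, data management, study implementation, study monitoring, and data analysis and reporting".

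On the primary analysis, 12.1 and 12.4.1 specify a repeated-measures ANOVA with group and time as factors. Section 12.4.1 then adds: "In the event of significant loss to follow-up, we will explore the use of a linear mixed model". No amount of loss is given as the trigger.

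**The concern.** Blinding has work to do after the last pain score is collected. Someone still decides whether a late complaint is an adverse event, how severe it is and whether treatment caused it. Someone resolves queries and corrects entries, and someone settles the parts of the analysis that the plan leaves open. Under 7.11 as written, all of this may be done by people who know the arms.

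Two comparisons are exposed. One is the between-arm comparison of adverse-event proportions in 12.1, which depends on judged events. The other is the primary VAS comparison, through late data corrections and the choice of model and deciding term. If the analysis were fully fixed in advance, early unblinding would matter less. Here the open choices and the early trigger coincide.

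**Working it through.** The point is mainly procedural, so the check sets the sections side by side.

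1. **The plan's own figure.** Section 12.1 claims more than 90% power for a difference of 1.0, SD 1.5, two-sided 0.05, with 10% attrition. The noncentrality is 1.0 / (1.5 × √(2/n)). With n = 55 per arm this is 3.50, and power is 93.4%. With 55 × 0.9 = 49.5 per arm it is 3.32, and power is 90.7%. The claim reproduces, and unblinding timing does not change it.

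2. **When follow-up ends.** Section 7.9 ends a subject's follow-up when all scheduled appointments are complete, and 7.10 puts follow-up at 3 months after treatment. On that reading, the team trigger in 7.11 is met on the day of the last participant's 3-month visit.

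3. **What is still running that day.**
   - Section 13.4 records non-serious events for 7 days, and serious events for 30 days, after the last day of participation.
   - Section 13.3 follows every reported event to resolution or stabilization, possibly after participation ends. Section 7.10 says the same for subjects removed because of unacceptable events.
   - Section 13.1.2 requires a CTCAE grade and a five-level attribution to treatment. Section 13.4 makes severity and relationship clinical judgments.
   - Site staff enter the data (11.1). No point is set at which cleaning must be finished.

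4. **How many participants have an open window.** Assume even accrual, visits on schedule and unblinding at the earliest permitted day. Section 12.2 gives 110 subjects in 18 months: 110 / 18 = 6.11 per month. A month is 365 / 12 = 30.4 days.
   - Serious-event window: 6.11 × 30 / 30.4 = 6.0 participants, or 6.0 / 110 = 5.5%.
   - Non-serious window: 6.11 × 7 / 30.4 = 1.4 participants, or 1.4 / 110 = 1.3%.
   - These count participants with an open window, not events. Earlier events still unresolved come on top, and the documents give no basis for counting them.

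5. **What is still open in the analysis.** Three primary choices are not settled: how much loss to follow-up is significant; whether ANOVA or the mixed model is then primary; and whether the group term or the group-by-time term answers the primary question (12.1, 12.4.1). Section 12.1 also leaves the pairs of time points for the within-arm tests unnamed.

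6. **Who holds the list.** One division made the schema (7.11) and assists with data management and analysis (12.1). No blinded and unblinded roles within it are described. The names are removed, so the text does not show whether they are the same people.

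**The case against.** The strongest reply is that 7.11 sets an earliest point, not a date. Unblinding after cleaning and lock would comply with it, so the plan is silent about a lock rather than opposed to one. That is correct. Follow-up could also be read to include adverse-event follow-up, and the participant trigger does wait for data collection to finish. That reading would close the adverse-event gap for the team, but not the gap for cleaning and model choice.

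Existing safeguards also count. The primary outcome is the participant's own mark on a 10 cm line (3.1), collected while the team is blinded. REDCap keeps an audit trail (11.1.1), which makes late edits traceable though not blind. Events are reported to the DSMB as they occur, with severity and relationship (14), so most grading should precede unblinding. Attrition can be judged without knowing arms.

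Three stronger readings are tempting, and the documents do not support them:

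- **The list makers are the analysts.** The shared division and paired names make this likely, but the names are removed and 12.1 speaks of assisting. Only the lack of a described separation is certain.
- **A type I error can be attached.** Choosing freely between two independent 5% tests gives 1 − 0.95² = 9.75%. That measures an unnamed primary contrast, not unblinding timing. It would remain after a lock if the contrast were still unnamed, and would vanish with a named contrast whatever the unblinding date. Larger figures that add between-arm tests at each visit use tests the plan does not contain, since the paired tests in 12.1 are within arm.
- **Blinding fails for the primary outcome.** Scheduled VAS collection remains protected.

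**Conclusion.** The point holds in limited form. Section 7.11 states an unblinding rule that, followed as written, permits late adverse-event assessment, data cleaning and primary-model choices with arms known. The adverse-event part rests on reading the end of follow-up as the last scheduled visit, as 7.9 does. The cleaning and analysis part holds on either reading.

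The exposure is small for late events: about 6 of 110 participants with an open serious-event window and 1 to 2 with an open non-serious window, under even accrual and earliest unblinding. It is unquantified for cleaning and analysis choices. This is an opportunity for bias, not evidence of it. Sample size, power and alpha are unaffected. It is a cheap improvement worth making.

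**What to change.** In 7.11, replace both end-of-study triggers with one. Neither the study team nor participants are unblinded until:

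- the adverse-event recording windows in 13.4 have closed for every participant;
- all queries are resolved and the database is locked; and
- the analysis sets, primary contrast and model, including a stated threshold for moving to the mixed model, are signed off and dated.

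Follow-up of unresolved events under 13.3 can continue after lock; only the recording windows need to have closed.

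Keeping the participant-to-arm link in the pharmacy would not blind the list makers, who already know the schema. The dated sign-off is therefore the main safeguard, and it should be made before anyone sees outcome data by arm. Section 7.11 should also state whether those who made the schema are separate from those who manage and analyse the data.

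The cost is about two sentences for the trigger, one more for the roles, and no added staff. The downside is a delay of some weeks before the team is unblinded and participants learn their treatment.

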7.12 Study Intervention/Follow-up Compliance

Not applicable

8. Study Intervention Discontinuation and Participant Discontinuation/Withdrawal

8.1 Discontinuation of Study Intervention

There is only one study intervention, injection of BTA or placebo, so there will be no discontinuation of the study intervention.

8.2 Participant Discontinuation/Withdrawal from the Study

Participants are free to withdraw from participation in the study at any time upon request.

An investigator may discontinue or withdraw a participant from the study for the following reasons:

- If any clinical adverse event (AE), laboratory abnormality, or other medical condition or situation occurs such that continued participation in the study would not be in the best interest of the participant
- If the participant meets an exclusion criterion (either newly developed or not previously recognized) that precludes further study participation
- Participant lost to follow-up after several attempts to contact subject to schedule study visit.

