4.3 Exclusion Criteria

- 1. Baseline pain measured by the subject < 3.5/10 on visual analog scale
- 2. Central/neuropathic pain disorder affecting the masticatory muscles
- 3. Temporomandibular joint arthralgia that is more severe than the myofascial pain disorder affecting the masticatory muscles
- 4. Previous temporomandibular joint surgery
- 5. Systemic arthropathies
- 6. Fibromyalgia
- 7. Allergy to study medications
- 8. Traumatic injury of masticatory muscles or temporomandibular joint within last 12 months
- 9. Mandibular fracture within the last 12 months
- 10. Pregnancy or breastfeeding
- 11. Cervical radiculopathy or surgery
- 12. Prior Botox injection in the masticatory muscles
- 13. Initiation of additional treatment of MPD within the past 3 months

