7.9 Duration of Therapy and Criteria for Removal from Study

Study Termination Guidelines: A subject's follow-up in the study will end after one of the follow applies:

- Subject's voluntary withdrawal
- Subject lost to follow-up
- Subject death
- Completion of all scheduled study follow-up appointments

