12.1 Study Design/Endpoints

Based on the preliminary data and the sample size calculations estimating a difference in mean prepost VAS change between groups of 1 point or greater (on a scale of 1-10), we plan to enroll a total of 110 subjects between the two study sites. Estimated 55 subjects will be enrolled at Weill-Cornell Medical Center/ New York Presbyterian Hospital and 55 subjects will be enrolled at the University of Illinois at Chicago. With 55 patients in the botulinum toxin A injection group and 55 patients in the placebo group (N=110), the study will have more than 90% power to detect a difference in mean in pre-post change between groups of 1.0 point or greater on VAS, using a two-sided t-test and assuming a standard deviation of 1.5 for the mean difference. This calculation allows for 10% attrition rate.

An intent-to-treat design will be followed and all subjects will have scheduled outcome evaluations until the end of the study, death of the subject, or subject refusal. Subjects will be withdrawn from their randomly assigned treatment for considerations of subject safety only. Descriptive statistics including mean, standard deviation, median, range, frequency, and percent will be calculated for the entire cohort as well as by the study arm (botulinum toxin A and unpreserved 0.9% sodium chloride) to assess the results of randomization and identify potential confounders.

The primary analyses of the data will be performed according to subjects' original treatment assignment (i.e., intention-to-treat analyses) and the inclusion of all data from all subjects randomized in the final analysis. To assess the primary endpoint of improvement of pain on a visual analog scale (VAS) between pre-op, 1, 2, and 3 months post-op, a repeated measure of analysis of variance will be performed with one between subject factor (botulinum toxin A versus placebo) and one within subject factor (time). This analysis will also be used for the secondary endpoints: function (MIO/jaw limitation scale) and quality of life (SF12). In the event of significant loss to follow-up, we will explore the use of a linear mixed model to assess the independent effect of the study group on VAS over the study visits. The paired t-test, or the signed-rank test as appropriate, will be used to assess change in pain, function, and QOL between pairs of relevant time points for both study arms.

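### Section 8.2 could let an investigator end outcome collection when an exclusion criterion newly develops, in conflict with the follow-up of all subjects promised in 12.1

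*Combined protocol and SAP*

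**What the plan says.** Section 8.2 states: "An investigator may discontinue or withdraw a participant from the study for the following reasons". The second reason on the list is: "If the participant meets an exclusion criterion (either newly developed or not previously recognized) that precludes further study participation". The list of exclusion criteria in 4.3 ends with criterion 13: "Initiation of additional treatment of MPD within the past 3 months".

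Section 12.1 adopts an intention-to-treat design in which "all subjects will have scheduled outcome evaluations until the end of the study, death of the subject, or subject refusal". It specifies "the inclusion of all data from all subjects randomized in the final analysis".

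Section 7.9 introduces its list with "A subject's follow-up in the study will end after one of the follow applies" and names voluntary withdrawal, loss to follow-up, death and completion of visits. Section 7.10 says: "Subjects will be followed for 3-months after receiving treatment or until death, whichever occurs first". It adds that patients removed for unacceptable adverse events are followed until the event resolves or stabilises.

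Section 8.1 notes that there is one injection and so nothing to discontinue. Section 7.8 asks only that concomitant medications be recorded. No section says whether VAS visits continue after a withdrawal under 8.2.

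**The concern.** Under 12.1 a randomised patient is assessed to month 3 unless he or she dies or refuses. Under 8.2 the investigator may take the patient out of the study for a reason that is neither of these and need not concern safety. Two sites could treat the same patient differently, and each could cite the protocol.

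The exit costs information and gains nothing in return. The drug has already been given, so withdrawal cannot spare the patient any exposure; it only ends the pain, function and quality-of-life measurements.

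The most awkward case is criterion 13. A patient who adds MPD treatment after injection may well be one whose pain has not improved. Under the trial hypothesis in 3.1, more such patients would be on placebo. If they are withdrawn, missingness depends on both arm and outcome. The remaining placebo patients then look better than the whole placebo arm, and the estimated benefit shrinks.

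**Working it through.** **1. The four sections side by side**

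| Section | What ends outcome follow-up | Exit for a newly met exclusion criterion? |
|---|---|---|
| 7.9 | voluntary withdrawal, loss to follow-up, death, completion | not listed |
| 7.10 | three months or death; removal for unacceptable adverse events is mentioned | not listed |
| 8.2 | investigator's discretion: medical or safety grounds, exclusion criterion, loss to follow-up | yes |
| 12.1 | end of study, death, refusal | not listed |

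Criterion 13 looks back three months and follow-up lasts three months. Any MPD treatment started after injection would therefore fall inside that window at every later visit.

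**2. The plan's own power figure**

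Inputs from 12.1: difference 1.0, SD 1.5, 55 per arm, two-sided 0.05, 10% attrition.

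Power ≈ Φ(Δ/SE − 1.96), with SE = SD·√(2/n).

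- n = 55: SE = 1.5·√(2/55) = 0.286, and Φ(3.496 − 1.96) = 93.8% (noncentral t: 93.4%).
- n = 55 × 0.9 = 49.5: SE = 0.302, and Φ(3.317 − 1.96) = 91.3% (noncentral t: 90.7%).

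The stated power above 90% reproduces. The margin is thin: by the same formula, 20% attrition gives 87.8% and 30% gives 83.3%, before any bias.

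**3. Illustration of selective withdrawal**

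Only Δ = 1.0 and SD = 1.5 come from the documents. The following are assumptions:

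- mean improvement 1.0 on placebo and 2.0 on Botox at each visit, normally distributed;
- correlation ρ = 0.5 between visits;
- a patient whose month-1 improvement is below c is withdrawn after that visit with probability r.

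With a = (c − μ)/1.5, the fraction lost is r·Φ(a). The mean month-3 improvement of those who stay exceeds μ by ρ·1.5·r·φ(a)/(1 − r·Φ(a)).

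For c = 0.5:

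- Placebo: a = −0.333, Φ = 0.3694, φ = 0.3774.
- Botox: a = −1, Φ = 0.1587, φ = 0.2420.
- r = 0.5: losses 18.5% and 7.9%. Upward shifts are 0.75 × 0.5 × 0.3774/0.8153 = 0.174 and 0.75 × 0.5 × 0.2420/0.9207 = 0.099. Completer difference = 1 − 0.174 + 0.099 = 0.925.
- r = 0.8: losses 29.6% and 12.7%; shifts 0.321 and 0.166; completer difference 0.845.

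Month-3 completer difference over all settings:

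| r | c = 0 | c = 0.5 | c = 1.0 |
|---|---|---|---|
| 0.3 | 0.960 | 0.962 | 0.972 |
| 0.5 | 0.927 | 0.925 | 0.938 |
| 0.8 | 0.866 | 0.845 | 0.841 |

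For complete cases averaged over the three visits, ρ is replaced by (1 + 0.5 + 0.5)/3 = 0.667. At c = 0.5 the difference is then 0.90 (r = 0.5) or 0.79 (r = 0.8).

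Power for the month-3 comparison at c = 0.5, holding SD at 1.5:

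- r = 0.5: 44.8 and 50.6 patients remain, SE = 0.308, Φ(0.925/0.308 − 1.96) = 85%.
- r = 0.8: 38.7 and 48.0 remain, SE = 0.324, Φ(0.845/0.324 − 1.96) = 74%.

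Simulation with 4,000 trials per setting gave 86% and 77%. Both figures are before ordinary dropout.

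**4. Two checks on what drives the bias**

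- If the worst 10% are removed from both arms alike, the difference stays at 1.0. The bias comes from unequal removal.
- An estimate that uses everyone's month-1 value and the month-1 to month-3 regression returned 0.99 to 1.01 in all nine settings. Withdrawal here depends only on an observed value, so a likelihood-based model can recover the full difference.

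**The case against.** The strongest objection is that 8.2 says less than it might seem to. It is permissive, and it covers only a criterion that precludes further participation. The documents never say that criterion 13 does so. The exclusion list is written for screening. Read literally after injection, criterion 12 (prior Botox in the masticatory muscles) would catch every treated Botox patient, so some selection among the criteria must be meant. Recording medication changes throughout follow-up (7.8) also fits with keeping such patients. All of this stands: 8.2 could allow these withdrawals but does not require them. It does not remove the conflict, because the qualifier is undefined and the choice is left to each investigator.

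A reader might also cite the 12.1 sentence "Subjects will be withdrawn from their randomly assigned treatment for considerations of subject safety only" as a second contradiction. It does not serve: it concerns assigned treatment, which is one injection already given. The silence of 7.9 is weak evidence too, since 7.10 already recognises a removal reason that 7.9 omits. The conflict rests mainly on the 12.1 sentence about outcome evaluations.

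On size, nothing in the documents supports any particular removal rate. At r = 0.5 and c = 0.5 the shift of 0.075 is about a quarter of the standard error of 0.308. The plan also names a linear mixed model, which would largely correct the loss modelled here. That stands in part. The primary method is repeated-measures ANOVA, which as usually run drops patients with a missing visit. The mixed model is only to be explored after significant loss, and no threshold is given.

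**Conclusion.** Wrong as written, as an internal contradiction: 8.2 permits an investigator-decided exit that need not be for safety, and 12.1 does not allow it. Confidence in the contradiction is high.

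Confidence in the size of the bias is low to moderate. With a true difference of 1.0, the month-3 completer difference is about 0.93 to 0.97 at 30-50% removal of poor month-1 responders and about 0.84 to 0.87 at 80%. This rests on assumed removal rates, an assumed visit correlation, more poor responders on placebo, and a complete-case analysis.

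A reader might infer that 8.2 does remove non-responders, or that it could produce a false positive. The documents support neither. That patients who start new MPD treatment are non-responders, and that investigators would withdraw them, are reasonable inferences but are not stated. Under the plan's hypothesis the bias runs toward no effect, so the risk is an understated or missed benefit.

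Whether new MPD treatment should be allowed after injection is a clinical matter, and no position is taken on it.

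**What to change.** Reconcile 7.9, 7.10, 8.2 and 12.1. State in 8.2 that a participant who meets an exclusion criterion after injection keeps all scheduled outcome visits and stays in the primary analysis unless he or she refuses, and align the other sections with that. Leave the safety bullet in 8.2 unchanged.

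Report new MPD treatment by arm from the follow-up form that already records concomitant medications. Section 7.8 mentions only medications, so confirm that the form also captures non-drug treatment such as night guards and physical therapy.

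The cost is a wording amendment with ethics approval. The visits are already in the schedule of assessments, and the sample size does not change.
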